**Secondary Objective:**

- To evaluate the safety and tolerability of weekly MOD-4023 administration.
- To demonstrate successful operation (single injection) of the MOD-4023 single patient use, multi-dose, disposable pre-filled pen (PEN).
- Evaluation of participant and observer feedback on MOD-4023 device usability.
- To confirm the correct operation of devices returned for evaluation.

**LT-OLE Objective:**

- To demonstrate LT safety and efficacy of MOD-4023 in an OLE.

**Other Objectives:**

To evaluate the effect of weekly MOD-4023 and daily Genotropin® administration on QoL, as measured by the QoLISSY in a specific number of countries (determined by availability of validated translated tools) during the first 12 months of treatment.

**3. STUDY DESIGN**

The study will consist of 12 months, open-label, multi-center, randomized, active controlled, parallel group study comparing efficacy and safety of weekly MOD-4023 to daily GH, Genotropin®.

Both drugs will be injected using a PEN device.

The study will be divided into two parts:

**Main Study Period (main study):** After an 8 wk screening perioda, patients meeting the eligibility criteria, as approved by global study MM, will be randomized in a 1:1 ratio to weekly SC doses of MOD-4023 (investigational treatment) or daily SC administration of Genotropin® (reference therapy) for 12 months. The key safety data will be reviewed by an independent DSMB every 4 months or on an *ad hoc* basis.

**LT-OLE Period (LT-OLE):** Patients who received MOD-4023 during the main study will continue in the LT-OLE with the same dose (mg/kg/wk) of MOD-4023. Patients who received Genotropin® during the main study will be switched to MOD-4023 and will begin treatment with a dose of 0.66 mg/kg/wk beginning no less than one day after cessation of Genotropin® treatment. The key safety data will be reviewed by an independent DSMB approximately every 6 months.

During the entire study (main study and LT-OLE), the dose of MOD-4023 and Genotropin® will be adjusted every 3 months based on the patient's body weight. Doses may be decreased for safety reasons according to the pre-defined dose-adjustment criteria (which will be based on the severity

a If the patient's screening process is delayed because of a benign illness or unforeseen benign condition (i.e. pharyngitis, viral GI problems, minor accident or trauma, etc.) or other technical issue that is related screening procedures (for example, delays with laboratory results) extra time will be added to the duration of the screening period, but not in excess of an additional four wks (total of 12 wks screening period).

of AEs or repeated, elevated levels of IGF-1). The dose will be decreased based on two, repeated day 4(-1) post-dose levels of IGF-1 SDS  $\geq +2.0$  (Section 6.4). During the LT-OLE, dose reduction for IGF-1 level  $>+2.0$  SDS will be made following consultation with the Global Study MM on an individual patient basis

The total duration of patient participation in the main study will be up to 15 months (12 months of treatment, up to eighta (+4) wks of screening and one month post dosing EOS follow up for patients not continuing in the LT-OLE, discontinued early or following study closure).

The LT-OLE will continue until marketing approval.

The study will be conducted at approximately 200 sites in 30-40 countries worldwide.

## 4. STUDY POPULATION

Pre-pubertal children (boys 3-11 years, girls 3-10 years), diagnosed with GHD.

### 4.1 INCLUSION CRITERIA

Patients must meet all inclusion criteria to be eligible for the main study:

1. Pre-pubertal children aged  $\geq 3$  yrs old and not yet 11 years for girls (10 years and 364 days) or not yet 12 years (11 years and 364 days) for boys (on the date of ICF signature) with either isolated GHD, or GH insufficiency as part of multiple pituitary hormone deficiencies.
2. Confirmed diagnosis of GHD by 2 different GH provocation tests defined as a peak plasma GH level of  $\leq 10$  ng/ml, determined by local (if done prior to signing the ICF) or central laboratory using a validated assaya. Prior local laboratory results will be accepted subject to pre-approval by global study MM and if the tests were conducted according to one of the protocols in [Appendix Bb](#).
3. BA is not older than CA and should be  $< 10$  for females and  $< 11$  for males.
4. No prior exposure to any r-hGH therapy.
5. Impaired Ht and HV defined as:
  - Annualized HV below the 25th percentile for CA (HV  $< -0.7$  SDS) and gender according to the OPKO HV (Tanner, Prader and Hermanussen) calculator, provided.
  - The interval between 2 Ht measurements should be at least 6 months, but should not exceed 18 months prior to inclusion.
6. Baseline IGF-1 level of at least 1 SD below the mean IGF-1 level standardized for age and sex (IGF-1 SDS  $\leq -1$ )c according to the central laboratory reference values. A single re-test will be allowed (subject to discussion with MM) if all other criteria are met.
7. Normal calculated GFR based on updated “bedside” Schwartz formula for pediatric patients (recommended calculation is provided below):
 
$$\text{CrCL (mL/min/1.73 m}^2\text{)} = 0.413 * \text{Ht} / \text{Scr};$$

Ht: in cm;  
Scr: mg/dL;

a ITT, with serum cortisol response to hypoglycemia if insulin stimulation test is chosen / Arginine test / Clonidine test / Glucagon test / L-dopa test.

b Prior spontaneous nocturnal GH secretion should be  $\leq 10$  ng/mL.

c According to rounding policy IGF-1 results  $\leq -0.95$  **might** be acceptable as well.

Effective Date: Date of final electronic approval

8. Children with multiple hormonal deficiencies must be on stable replacement therapies (no change in dose) for other hypothalamo-pituitary-organ axes for at least 3 months prior ICF signing.
9. Normal 46XX karyotype for girls.
10. Willing and able to provide written informed consent of the parent or legal guardian of the patient and written assent from pediatric patients (where applicable based on age and country regulation).

#### Inclusion into the LT-OLE:

11. Completion of the main study (12 months of treatment) with adequate compliance.
12. Willing and able to provide written informed consent of the parent or legal guardian of the patient and written assent from pediatric patients (where applicable based on age and country regulation).
13. Agreement to refrain from sexual activity during the LT-OLE i.e. observe complete sexual abstinence as the only acceptable contraceptive measure during the LT-OLE (for pubertal and post-pubertal patients).

#### **4.2 EXCLUSION CRITERIA**

1. Children with prior history of leukemia, lymphoma, sarcoma or any other form of cancer.
2. History of radiation therapy or chemotherapy.
3. Malnourished children defined as BMI <-2 SDS for age and sex.
4. Children with psychosocial dwarfism.
5. Children born small for gestational age (SGA – birth weight and/or birth length <-2 SDS for gestational age).
6. Presence of anti-hGH Ab at screening.
7. Any CS abnormality likely to affect growth or the ability to evaluate growth, such as, but not limited to, chronic diseases like renal insufficiency, spinal cord irradiation, etc.
8. T2 and T1 diabetic patients, who in the opinion of the investigator are not receiving standard of care treatment or are non-compliant with their prescribed treatment or who are in poor metabolic control. Criteria for controlled diabetes are defined in [Appendix F](#).
9. Chromosomal abnormalities including Turner's syndrome, Laron syndrome, Noonan syndrome, Prader-Willi syndrome, Russell-Silver syndrome, SHOX mutations/deletions and skeletal dysplasias.
10. Concomitant administration of other treatments that may have an effect on growth such as anabolic steroids, or sex steroids, with the exception of ADHD drugs or hormone replacement therapies (thyroxin, hydrocortisone, desmopressin [DDAVP®]).
11. Children requiring glucocorticoid therapy (e.g. for asthma) that are taking chronically a dose greater than 400 µg/day of inhaled budesonide or equivalent as described in [Appendix J](#).
12. Major medical conditions and/or presence of contraindication to r-hGH treatment.
13. More than 1 closed epiphyses.
14. Known or suspected HIV-positive patient, or patient with advanced diseases such as AIDS or tuberculosis.
15. Drug, substance, or alcohol abuse.

Effective Date: Date of final electronic approval

16. Known hypersensitivity to the components of study medication.
17. Other causes of short stature such as celiac disease, uncontrolled primary hypothyroidism and rickets.
18. The patient and/or the parent/legal guardian are likely to be non-compliant in respect to study conduct.
19. Participation in any other study of an investigational agent within 30 days prior to ICF signature (including administration of investigational agent).
20. Study enrollment requirements have been met or the study has been closed by the Sponsor prior to the completion of screening process.

Exclusion during the LT-OLE:

21. Concomitant administration of other treatments that may have an effect on growth such as anabolic steroids, or sex steroids (other than for hormonal replacement), with the exception of ADHD drugs or hormone replacement therapies (thyroxin, hydrocortisone, testosterone, estrogen/progesterone, desmopressin [DDAVP®])
22. Change in medical condition during the treatment period (such as, but not limited to, development of a serious inter-current critical illness, a severe adverse drug reaction, etc.)
23. Positive pregnancy test.
24. Unresolved drug related (MOD-4023 or Genotropin®) SAE from the treatment period as per MM judgement.

**4.3 PATIENT IDENTIFICATION**

A unique identification number will be assigned by the Electronic Data Capture (EDC) system when an individual patient or their legal guardian or parent signs the ICF and starts the screening process. Following eligibility confirmation by global study MM, the patient will be randomized through the Interactive Web Response Technology system (IRT). The randomization will be stratified based on:

1. Geographical region (1. Western Europe, Israel, Australia, New Zealand, Canada and USA; 2. Central and Eastern Europe, Greece, Turkey, Latin America, Asia except for India and Vietnam; 3. India and Vietnam);
2. GH peak levels at Screening  $\leq 3$  ng/mL;  $>3$  to  $\leq 7$  ng/mL; and  $>7$  to  $\leq 10$  ng/mL; and
3. CA (3-7 and 0 days, above 7).

The unique identification number assigned during the main study will continue to be used in the LT-OLE.

**4.4 REMOVAL, REPLACEMENT, OR EARLY WITHDRAWAL OF PATIENTS FROM THERAPY OR ASSESSMENT**

Patients are free to discontinue their participation in the study at any time and without prejudice to further treatment. The investigator must withdraw any patient from the study if that patient or parent/legal guardian requests to be withdrawn. Patients withdrawn from the study during the 12 months of treatment post first dose will not be replaced. Those patients withdrawn who have successfully completed screening, but prior to first dose, will be replaced.

The patient's participation in this study may be discontinued due to the following reasons:

- Request from regulatory agency, sponsor, primary care physician, or Investigator.
- Withdrawal of the patient's/parent's/legal guardian's consent for any additional study participation or procedure, including lost to follow up (with specific withdrawal reason collected, as possible).
- AE:
  - Occurrence of a malignancy during the course of the study.
  - Development of serious intercurrent critical illness.
  - Development of benign intracranial hypertension, if the symptoms return following resumption of drug (after a temporary stop).
  - Occurrence of AEs following which the Investigator, or the patient wishes to discontinue treatment (such as, but not limited to, slipped capital femoral epiphysis, scoliosis, avascular necrosis and development of lipoatrophy, etc.).
- Intake of prohibited concomitant medication (in consultation with the MM).
- Investigator decides that withdrawal from the study is in the best interest of the patient e.g. patient non-compliance, occurrence of neutralizing Ab, protocol deviation(s) (including protocol deviation(s) that affect patient safety and accuracy, and/or validity of data) etc.
- Any clinically significant change in the patient's medical condition.

During the LT-OLE:

- Girls with a BA of  $\geq 13.5$  years and boys with a BA of  $\geq 16$  years.
- Positive urine pregnancy test or confirmed pregnancy. In case of pregnancy, the study drug should be discontinued, and the Global Study MM be alerted immediately. All pregnancy tests used in this study, either urine or serum, must have a sensitivity of at least 25 mIU/mL and must be performed by a certified laboratory. Pregnancy tests will also be done whenever one menstrual cycle is missed during treatment (main study and LT-OLE) and when potential pregnancy is otherwise suspected and may be repeated if requested by institutional review boards (IRBs)/ethics committees (ECs) or if required by local regulations. In the case of a positive confirmed pregnancy, the patient will be withdrawn from administration of investigational product but may remain in the study for follow up.
- When the patient's annualized growth rate is  $\leq 2$  cm/12 months (the interval between two height measurements should be at least six months).

Patients can be re-screened for inclusion in the main study **one** time. Any data collected during the original screening period will be acceptable as historical data, EXCEPT safety laboratory data and IGF-1 and IGFBP-3 levels, which must be repeated and evaluated for eligibility. In this case, the patient will be assigned a new screening number.

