**4.5 HANDLING OF WITHDRAWALS**

If a patient is withdrawn from the study or fails to return either at his or her request or at the investigator's discretion after randomization, every effort should be made to determine the reason. This information will be recorded on the patient's electronic case report form (eCRF). All patients who withdraw from the study prematurely, regardless of cause, should undergo all early termination assessments (see Section 5.5). It is vital to obtain follow-up data for any patient withdrawn due to an AE or abnormal laboratory test finding. In any case, every effort must be

made to undertake safety follow-up procedures. If a patient wishes to withdraw, the difference between treatment discontinuation and study withdrawal will be explained. Patients should be encouraged to continue the follow up visits and at minimum provide a Ht measurement at 12 months of the initial treatment period even if they discontinue the study treatment early.

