### 5.5 EARLY DISCONTINUATION STUDY VISIT

If, during the main study, a patient discontinues prematurely from the study for the reasons specified in Section 4.4, the same procedures planned for Visit 8 (12 months/Wk 52 [ $\pm$ 1 wk]) will be conducted. Other procedures and evaluations will be completed as deemed necessary by the Investigator.

If, during the LT-OLE, a patient discontinues prematurely from the study for the reasons specified in Section 4.4, the same procedures for LT-OLE EOS/ET will be conducted.

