#### 6.9.4 Prohibited Concomitant Medication

The following medications are not permitted during the study and may lead to withdrawal of the patient from the study:

- Any hormonally active medication other than replacement therapy for pituitary failure. Glucocorticoid replacement dosing should be carefully adjusted in children receiving MOD-4023 and Genotropin® and glucocorticoid treatments to avoid both hypoadrenalism and an inhibitory effect on growth.
- Any new long-term glucocorticoid treatment should be noted on the concomitant medication form and the patient should be retained in the safety population, but not the per-protocol population. Short term glucocorticoid treatment is allowed.
- Anabolic steroids (including testosterone replacement therapy) should not be taken.
- Weight loss drugs.
- Psychiatric medications typically associated with weight changes and/or diabetes excluding medications used to treat ADHD.

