## 8. STATISTICAL ANALYSIS METHOD

### 8.1 SAMPLE SIZE CONSIDERATION

The aim of the main study is to demonstrate that weekly MOD-4023 is not inferior to daily r-hGH administration. Non-inferiority will be claimed if the 2-sided 95% CI for mean treatment difference (MOD-4023 – Genotropin®) in the primary efficacy endpoint will lie entirely above “non-inferiority margin” of -1.8 cm/year.

The following assumptions were made in the sample size calculation:

- 2-sided alpha of 0.05.
- 80 % power.
- Between-patient SD of annual growth rate is 2.5 cm/year in all treatment groups.
- Non-inferiority margin is -1.8 cm/year.
- The true mean treatment difference (MOD-4023 – Genotropin®) is -0.8 cm/year.

With these assumptions, 100 patients per group will provide 80 % power for the non-inferiority test. To allow for an approximate 10 % dropout rate, 110 patients will be randomized to each treatment group (Total N=220 patients).

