#### 8.2.2 Full Analysis Set

The full analysis set will include all patients randomized and will be the primary efficacy analysis set. Patients will be analyzed according to randomized treatment group.

If study enrollment is closed prior to subject full qualification and/or study closure for any other reason by the Sponsor and/or patients lost to follow up between Visit 1 and Visit 2, the patient will be excluded from the study.

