### 8.3 HANDLING OF MISSING DATA

The method for handling missing data will be described in the SAP. The primary method of imputation will be with multiple imputation assuming missing at random, using SAS PROC MI. Details on all sensitivity analyses related to the handling of missing data will also be provided in the SAP.

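### Investigator-initiated withdrawal from the study (4.4, 6.9.4) may leave the Week 52 height uncollected for growth-related reasons; the protocol should seek that height from every randomized child whose consent stands

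*Protocol*

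**What the plan says.** **Withdrawal.** Protocol 4.4 lists reasons for which participation in the study may be discontinued. One is prohibited concomitant medication, in consultation with the medical monitor. Another is discretionary: "Investigator decides that withdrawal from the study is in the best interest of the patient e.g. patient non-compliance, occurrence of neutralizing Ab, protocol deviation(s"). Section 6.9.4 says that use of prohibited medication "may lead to withdrawal of the patient from the study".

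**Follow-up.** Section 4.5 opens with withdrawals at the patient's request or at the investigator's discretion, and sends every premature withdrawal, whatever the cause, to the early termination assessments. It then says that the difference between stopping treatment and leaving the study is explained to a patient who wishes to withdraw. Its last sentence reads "Patients should be encouraged to continue the follow up visits and at minimum provide a Ht measurement at 12 months", and ties this to early discontinuation of study treatment. For a child who discontinues from the main study, 5.5 requires "the same procedures planned for Visit 8", which include a stadiometer height. It does not mention a later Week 52 measurement.

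**Analysis.** Section 8.2.2: "The full analysis set will include all patients randomized and will be the primary efficacy analysis set", by randomized group. Section 8.4.1 defines the primary endpoint from the heights and dates of Visit 2 and Visit 8. Section 8.3: "The primary method of imputation will be with multiple imputation assuming missing at random, using SAS PROC MI". The sensitivity analyses named in 8.6.2 are mITT, per protocol and LOCF; 8.3 defers the remaining missing-data analyses to the SAP. The SAP available covers only the open-label extension.

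**The concern.** Analysing all randomized children by randomized group, and asking for a 12-month height after treatment stops, together pose a question about growth regardless of adherence. Withdrawal from the study on grounds such as non-compliance or neutralizing antibody works against that, because no sentence clearly asks for a Week 52 height from a child whom the investigator withdraws. A height is taken at the early-discontinuation visit, but it cannot show growth after that date.

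Poor adherence and neutralizing antibody are plausible causes of slower growth. If they lead to a missing Visit 8 height, the value is missing for a reason that may be related to the outcome. Imputation under missing at random can then overstate the mean of the arm that lost those children. Such losses largely cancel if they are equally frequent in both arms. If they are not, the estimated difference shifts, and with it the error rate of the non-inferiority test. The trial is open-label, so these discretionary decisions are made with the arm known.

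**Working it through.** **Inputs from Protocol 8.1.** "2-sided alpha of 0.05", so 0.025 one-sided; "Between-patient SD of annual growth rate is 2.5 cm/year in all treatment groups"; margin -1.8 cm/year; assumed true difference -0.8 cm/year; 100 per group for 80% power; about 10% dropout, so 110 randomized per group.

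**The plan's own figure.** The distance from the assumed difference to the margin is 1.8 - 0.8 = 1.0 cm/year. n per group = 2 × (1.960 + 0.842)² × 2.5² / 1.0² = 98.1, rounded up to 99, against 100 stated. Power at 100 per group is 80.7%. The design reproduces.

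**Bias model.** Let d be the excess share of one arm whose Week 52 height is missing for these reasons, and s the amount in cm/year by which their true growth falls below the imputed value. That arm's mean is overstated by d × s. Neither d nor s is given in the documents; both are assumptions.

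SE = 2.5 × √(2/100) = 0.354 cm/year.

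One-sided error at a true difference of -1.8 = 1 - Φ(1.960 - bias/SE). Power at a true difference of -0.8 = 1 - Φ(1.960 - (1.0 + bias)/SE). Bias is positive when it favours MOD-4023.

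| Excess loss in | d | s (cm/year) | Bias (cm/year) | One-sided error | Power |
|---|---|---|---|---|---|
| MOD-4023 | 2% | 2.5 | +0.05 | 3.5% | 84.4% |
| MOD-4023 | 5% | 2 | +0.10 | 4.7% | 87.5% |
| MOD-4023 | 10% | 2 | +0.20 | 8.2% | 92.4% |
| Neither (equal losses) | any | any | 0 | 2.5% | 80.7% |
| Genotropin | 2% | 2.5 | -0.05 | 1.8% | 76.6% |
| Genotropin | 5% | 2 | -0.10 | 1.3% | 72.1% |
| Genotropin | 10% | 2 | -0.20 | 0.6% | 61.9% |

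**Bias that doubles the error.** (1.960 - 1.645) × 0.354 = 0.111 cm/year. At s = 2 cm/year this needs an excess loss of 0.111/2 = 5.6% on MOD-4023; at s = 2.5 it needs 0.111/2.5 = 4.5%.

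**Effect of interim heights.** The table assumes that none of the shortfall is visible to the imputation. A simulation allowed a month-9 value to inform it: 110 per arm, 4,000 runs, assumed month-9 to month-12 correlation 0.9, 10% loss on MOD-4023 only, shortfall 3 cm/year. One-sided error was 13.7% if none of the shortfall showed by month 9, 7.4% if half did and 3.2% if all did. Simulation error is about 0.3 to 0.5 percentage points.

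**The case against.** A reader might infer that these heights are lost and that the imputation favours non-inferiority. The documents do not support either statement.

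- **Not simply lost.** Withdrawal under 4.4 and 6.9.4 is discretionary. For new long-term glucocorticoid use, 6.9.4 keeps the child in the safety population and removes the child only from per protocol. Section 4.5 covers withdrawal at the investigator's discretion, sends every withdrawn child to early termination assessments that include height, and its 12-month request is a separate sentence that can be read broadly. It also calls follow-up data vital after withdrawal for an adverse event or abnormal laboratory finding. Nothing in 5.5 says that the early visit replaces Week 52. All of this stands, so the correct statement is that the heights may be lost.
- **Direction not shown.** Protocol 1.2 links daily injection to reduced compliance, so withdrawals for non-compliance could fall more on Genotropin and work against non-inferiority. Antibodies are tested in both arms. Against that, the main-study safety endpoints in 8.4.4 name neutralizing properties only for anti-MOD-4023 antibody, so that route plausibly falls more on MOD-4023. The net direction is unknown.
- **Imputation model unknown.** Section 8.3 does not say what enters the model. Heights at months 3, 6 and 9 and at early termination could absorb part of any bias. Without the main-study SAP, it cannot be said that no further missing-data analysis was planned.
- **Large scenarios may be remote.** An excess of 10% gives the whole planned dropout allowance to these reasons in one arm. In the phase 2 paediatric study described in 1.3.1, 52 of 53 treated children finished 12 months, a loss of 1/53 = 1.9% from all causes.

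What remains is the gap in wording. The 12-month height is encouraged rather than sought as a rule, it is phrased around stopping treatment, and it is not clearly tied to withdrawal initiated by the investigator.

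**Conclusion.** The concern holds as a gap in data collection, not as a demonstrated bias toward non-inferiority. Sections 4.4 and 6.9.4 permit study withdrawal for reasons that may relate to growth, and 4.5 and 5.5 do not secure a Week 52 height afterwards. Any missing value then enters an all-randomized analysis through imputation under missing at random.

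The size depends entirely on assumed loss shares and shortfalls. At an excess loss close to the phase 2 dropout (2%, with a 2.5 cm/year shortfall) on MOD-4023, the one-sided error is about 3.5%. A net bias of 0.11 cm/year brings it to 5%. The same losses on Genotropin reduce power instead. These figures are upper bounds in the sense that they give no credit to interim heights. No later sensitivity analysis can recover a height that was not measured, so a low-cost change to collection is worthwhile even though the likely effect is small.

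**What to change.** Reconcile Protocol 4.4, 4.5, 5.5 and 6.9.4 on two points.

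1. Distinguish stopping study drug from leaving the study wherever withdrawal is described. The protocol already does so for confirmed pregnancy (4.4, 5.10), where product is withdrawn but the patient may stay for follow-up.
2. State that a Week 52 height, dated from Visit 2, is sought from every randomized child whose consent or assent has not been withdrawn. This includes children withdrawn on the investigator's initiative, and the height is in addition to the early-discontinuation visit in 5.5.

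The change concerns data collection only. Decisions on when drug or participation is stopped for clinical reasons stay as written.

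The cost is protocol wording and a few extra site visits for children off drug. The Week 52 stadiometer measurement is already in the schedule.
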